For [Objective 2](#), that will compare patients who are being treated with dabigatran etexilate or VKA, a cohort design was selected to allow for comparisons between the two groups of patients regarding major and clinically relevant non-major bleeding events (primary safety outcome measure), and symptomatic recurrent DVT and PE events, including VTE-related mortality (primary effectiveness outcome measure). For the second objective, a balanced enrollment approach should be used so that the number of VKA patients does not vastly outnumber the dabigatran etexilate patients and both patient groups are collected at similar time points (i.e., for each dabigatran etexilate patient enrolled, the next VKA patient with the same index event (DVT/PE) should be recruited ideally at the same study site). Since the severity of the disease, treatment patterns and patient characteristics may differ considerably between patients with a DVT versus a PE, the treatment arms should have roughly equal numbers of patients with DVT and PE. To ensure global representation, regional recruitment caps will be employed to minimize under-or over-representation from a particular region. Patients should be enrolled ideally within 14 days but not more than 30 days of their acute VTE.

[figure not shown]

Figure 9.1:1 Study design

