#### 9.3.1.1 Baseline visit data points

The Flowchart (Table [9.3.1:1](#) and Table [9.3.1:2](#)) outlines all of the data points to be collected. No study procedures or data recorded in the EDC system should be performed unless the patient has consented to participate in the study or a waiver has been obtained in accordance with local regulations. As in any observational study, patients will be managed according to local clinical practice. The choice of treatment is solely at the discretion of the participating physicians. This means there are no additional medical or procedural risks to patients by

participating in this study. No additional medical procedures are required, over and above those that the patient would receive if not enrolled.

- Review of in- and exclusion criteria
- Demographic data will include year of birth, gender, race (as allowed by local regulations), insurance status
- Height, weight, blood pressure, and heart rate
- Available laboratory data (e.g., serum creatinine, hemoglobin, and INR)
- Information regarding the index VTE event including:
  - date of diagnosis,
  - risk factors for VTE (i.e., if the VTE was provoked or unprovoked),
  - clinical signs and symptoms and
  - the following variables based on objective testing (e.g. Venous compression ultrasonography, venography for DVT CT, MRI and any other examination that is deemed relevant per routine clinical practice for DVT diagnosis or ventilation-perfusion (V-Q) lung scan, pulmonary angiography or spiral (helical) computed tomography scan for PE):
    - Date of diagnostic testing
    - Location, extent and severity of venous thrombus
    - Impression or findings
- Treatment for VTE should include all treatment details including specific therapies provided for the event, start date(s) and stop dates (if applicable), dosage, planned treatment duration, and rationale for treatment choice.
- Medical history including current concomitant diseases, history of previous VTE (if any) risk factors (i.e., if the VTE was provoked or unprovoked) for VTE re-occurrence and risk factors for bleeding.
- Concomitant therapies that are being currently used by the patient including the name of the therapy and indication.

9.3.1.2 Hospital discharge or at 14 days after diagnosis of VTE event (whichever occurs later)

For [Objective 1](#), the additional data points will include:

- Any changes to the treatment for the VTE event
- Date of hospital discharge, if patient was admitted to hospital

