For [Objective 2](#), the additional data points will include:

- Any changes in VTE disease characteristics and/or treatment for the VTE event
- Concomitant diseases (current, any changes)
- Available laboratory data that is associated with outcome events (e.g., complete blood count (CBC) for major and clinically relevant non major bleeding events)
- INR for VKA patients
- Date of hospital discharge, if patient was admitted to hospital.
- Changes in concomitant therapies
- Information on any outcome events that may have occurred since study enrollment
- Adverse drug reactions

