The primary and further outcomes will be analyzed for dabigatran etexilate patients in comparison to VKA patients over 1 year. To support the sample size determination, assessments were performed for the primary safety outcome of major and clinically relevant non-major bleeding based on the observed event rate for VKA in the pooled analysis of the RE-COVER and RE-COVER II trials, and additional assumptions including a 1:1 ratio of dabigatran etexilate and VKA patients, one-year fixed follow-up, one-sided alpha of 0.025, and 15% loss to follow-up (Table [9.5:2](#)). With these assumptions, a total sample size of 5000

patients would provide 90% power to detect a hazard ratio of 0.69 between dabigatran etexilate and VKA.

Table 9.5:2 Sample size assessments for the primary safety outcome of major and clinically relevant non-major bleeding

Event rates		Hazard ratio	Power	Loss to follow-up	Total N
Dabigatran etexilate	VKA*				
5.3%	7.7%	0.69	90%	15%	5000
5.2%	7.7%	0.67			4500
5.1%	7.7%	0.65			4000
4.9%	7.7%	0.63			3500
4.7%	7.7%	0.60			3000

\* The VKA event rate is based on the pooled RE-COVER and RE-COVER II analysis of the oral treatment period [[P13-09153](#), [U12-3306-01](#)]. The Freedman formula was used for the calculations.

In combination with additional non-statistical considerations, a total sample size of up to 5000 patients (i.e., 2,500 patients per group) is deemed appropriate for the planned analyses for [Objective 2](#) on an exploratory basis. The actual power of the analysis will be dependent upon the actual rates of major bleeding and loss to follow-up in the current study, the covariates included in the statistical model, their degree of imbalance between the treatment groups, their strength of association with the outcome, and the use of propensity score matching, and may therefore be different.

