5.1 MAIN OUTCOMES

The main outcomes for Objective 2 are:

- Primary safety outcome measure: ISTH Major bleeding and ISTH clinically relevant non major bleeding (CRNMB)
- Primary effectiveness outcome measure: symptomatic recurrent VTE including VTE-related mortality

A patient is considered to have major bleeding if the bleeding is fatal and/or meets at least one of the following criteria:

- Overt bleeding associated with a reduction in hemoglobin of at least 20 grams per liter or leading to a transfusion of at least 2 units of blood or packed cells

- Symptomatic bleeding in a critical area or organ: intraocular, intracranial, intraspinal, or intramuscular with compartmental syndrome, retroperitoneal bleeding, intraarticular bleeding or pericardial bleeding

A patient is considered to have clinically relevant non major bleeding if the bleeding caused at least one of the following actions:

- Leading to hospitalization or increased the level of health care
- Requiring medical intervention by a healthcare professional
- Prompting a face to face evaluation

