Concomitant cancer	True or False (CRF categories, medical history and concomitant diseases will be manually reviewed (concomitant))	N/A
Antiphospholipid antibody syndrome	True or False (CRF categories, medical history and concomitant diseases will be manually reviewed (concomitant))	N/A
Polycythemia	True or False (CRF categories, medical history and concomitant diseases will be manually reviewed (concomitant))	N/A
Hypertension	True or False (CRF categories, medical history and concomitant diseases will be manually reviewed (concomitant))	N/A
History of previous VTE	True or False (CRF categories, medical history and concomitant diseases will be manually reviewed (regardless of timing))	N/A
Diabetes mellitus	True or False (CRF categories, medical history and concomitant diseases will be manually reviewed (concomitant))	N/A
Heart failure	True or False (CRF categories, medical history and concomitant diseases will be manually reviewed (regardless of	N/A

	timing))	
History of major bleeding	True or False (medical history and concomitant diseases will be manually reviewed (regardless of timing))	N/A
Stroke	True or False (CRF categories, medical history and concomitant diseases will be manually reviewed (regardless of timing))	N/A
Chronic hepatic disease	True or False (CRF categories, medical history and concomitant diseases will be manually reviewed (concomitant))	N/A
Chronic renal disease	True or False (CRF categories, medical history and concomitant diseases will be manually reviewed (concomitant))	N/A
Index event	DVT, PE, DVT and PE (CRF)	Very unlikely
Prior gastrointestinal bleed	True or False (CRF categories, medical history and concomitant diseases will be manually reviewed (regardless of timing))	N/A
Venous insufficiency or varicose veins	True or False (CRF categories, medical history and concomitant diseases will be manually reviewed (concomitant))	N/A

Overlap of estimated propensity scores

Overlap is the degree to which the ePS of the two treatment groups have a shared range. It is typically best examined graphically but will also be quantified by treatment group using the Kolmogorov Smirnov procedures [4] as a key quantitative indicator of the degree of overlap. To depict overlap in this context, a mirrored bar chart and overlapping line graphs of the estimated ePS of the two groups will be employed. One or both group distributions may be depicted before and after trimming. The same figure will be produced for logit transformed ePS.

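### Within each index-event type, the propensity model has no measure of acute severity or care setting, although the protocol collects several, so both main hazard ratios are open to avoidable confounding

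*SAP*

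**What the plan says.** The main analysis of both primary outcomes is a Cox model with overlap weights taken from the estimated propensity score (SAP for Objective 2, Section 7.6). The score uses the variables in Table 7.6: 1: demographics, BMI, creatinine clearance, region, smoking, alcohol, VTE risk factors, comorbidities, bleeding history and co-medication. The index VTE appears once, as "DVT, PE, DVT and PE (CRF". Table 7.6: 2, for the multivariable Cox sensitivity analysis, has no index-event row. SAP Section 6.5 keeps centre out of every analysis.

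The protocol collects more about the acute presentation:

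- Section 9.3.1.1 lists "Height, weight, blood pressure, and heart rate" at baseline, and the location, extent and severity of the thrombus from objective testing.
- Section 9.3.1.2 lists, for Objective 2, "Date of hospital discharge, if patient was admitted to hospital".

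SAP Section 7.9.3 plans only descriptive summaries of blood pressure and heart rate. Protocol Section 9.7.2.1 says the propensity model is to consider risk factors for VTE or bleeding and variables that influence the choice of anticoagulant. SAP Section 6.7 limits the model's covariates to data available up to the start of dabigatran or VKA.

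**The concern.** A patient admitted with a large PE and low blood pressure and a stable PE patient treated at home get the same index-event term. If prescribers choose between dabigatran and VKA partly on acute severity or care setting, the weights will not correct for it, except through correlated covariates such as cancer, heart failure or immobilization.

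Both main outcomes could be affected. The effectiveness outcome is "symptomatic recurrent VTE including VTE-related mortality", and severity of the index event may bear on death from VTE. The clinically relevant non-major bleeding criteria in SAP Section 5.1 turn on hospitalization or a higher level of care, medical intervention, or face-to-face evaluation. These may be easier to meet and record under closer observation, although that is an inference and not a statement in the documents.

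Sites range from general practices to hospitals (protocol Section 9.2), and Objective 2 enrolment is balanced on drug and index-event type only (Sections 9.1 and 9.2.4). The sensitivity analyses do not fill the gap: the multivariable Cox model holds less about the acute event than the main model, and the analysis without censoring at discontinuation reuses the main model.

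**Working it through.** **1. The planning figure, for scale.** This point disputes no number in the plan. Protocol Section 9.5 assumes "a 1:1 ratio of dabigatran etexilate and VKA patients, one-year fixed follow-up", "one-sided alpha of 0.025, and 15% loss to follow-up", and says that 5000 "patients would provide 90% power to detect a hazard ratio of 0.69 between dabigatran etexilate and VKA". The rates are 5.3% versus 7.7%, by the Freedman formula.

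- Events needed at HR 0.69: (1.960 + 1.282)² × (1.69/0.31)² = 10.51 × 29.72 ≈ 312.
- Treating the 15% loss as exponential dropout over the year, the mean observed event probability is about 0.0604. N = 312/0.0604 ≈ 5170.
- At N = 5000 the expected events are 5000 × 0.0604 ≈ 302, and power is Φ(√302 × 0.31/1.69 − 1.96) = 89.0%.
- Solving for the HR at N = 5000 gives 0.685, which rounds to 0.69. The plan's figure therefore reproduces.
- The standard error of the log HR at 302 events is 2/√302 ≈ 0.115. This ignores weighting, which would enlarge it, and applies to bleeding only. The protocol gives no planning effect for the effectiveness outcome.

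**2. What is collected and what is adjusted for.**

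| Item | Collected for Objective 2 | Table 7.6: 1 | Table 7.6: 2 |
|---|---|---|---|
| Index event type | yes | yes | no |
| Thrombus location, extent, severity | yes (protocol 9.3.1.1) | no | no |
| Blood pressure, heart rate | yes (protocol 9.3.1.1) | no | no |
| Index admission | derivable from discharge record (protocol 9.3.1.2) | no | no |

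**3. Size under assumed inputs.** The documents give neither admission rates by arm nor an admission–outcome association, so every input here is an assumption. For an omitted binary factor with event-rate ratio h and prevalences p_DE and p_VKA, a true HR of 1 reads approximately

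(1 + (h − 1)·p_DE) / (1 + (h − 1)·p_VKA).

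| h | 45% vs 60% admitted | 50% vs 60% admitted |
|---|---|---|
| 1.5 | 1.225/1.30 = 0.94 | 1.25/1.30 = 0.96 |
| 2.0 | 1.45/1.60 = 0.91 | 1.50/1.60 = 0.94 |
| 2.5 | 1.675/1.90 = 0.88 | 1.75/1.90 = 0.92 |

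Swapping the arms inverts these, giving 1.04 to 1.13. All are values before existing covariates absorb any of the imbalance.

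- On the log scale, 0.88 is 0.126/0.115 ≈ 1.1 standard errors and 0.96 is 0.039/0.115 ≈ 0.3.
- More extreme inputs give more. With 30% versus 60% and h = 3, the ratio is 1.6/2.2 = 0.73. Nothing in the documents says that such inputs are realistic.

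**4. The SAP's own balance measure.** By the dichotomous formula in Section 7.6, 45% versus 60% gives 0.15/√((0.2475 + 0.24)/2) = 0.30, above the 0.25 trigger. With 50% versus 60% it is 0.10/√((0.25 + 0.24)/2) = 0.20, below it. Either would be seen only if admission is among the covariates checked, and the visible text does not list them.

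**The case against.** Several points on the other side stand and limit the claim.

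- A reader might infer that the model has no severity measure at all. It has a coarse one, index-event type, along with cancer, heart failure, renal and hepatic disease, immobilization, trauma or surgery, and creatinine clearance. The gap is severity within event type.
- A reader might take the protocol to concede uncontrolled confounding by severity where it writes "Since the severity of the disease, treatment patterns and patient characteristics may differ considerably between patients with a DVT versus a PE". That sentence contrasts DVT with PE, and this contrast is in the propensity model and in the enrolment balancing.
- A reader might conclude that the balance table cannot show the problem. The SAP speaks of covariates of interest without restricting them to the propensity variables, and Sections 5.3, 6.4 and 7.7 are not in the public text. The supportable statement is that no visible text commits to checking these items.
- Blood pressure and heart rate are not ignored. They are summarised, but not used for adjustment.
- Vital signs may be recorded late. Baseline can span several contacts (protocol Section 9.2.4), with assessment up to 30 days after diagnosis (Section 9.2.1), so some values may follow stabilisation or first intake. Inpatient status at first intake would also partly reflect the treatment pathway, since some drugs follow parenteral lead-in.
- The analyses are declared exploratory (protocol Section 9.7.1), and follow-up starts at initiation of dabigatran or VKA (SAP Section 6.1), so events before that fall outside the comparison.

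The protocol also discloses that residual confounding may remain (Section 9.9). That does not answer this point: the disclosure concerns confounders that were not measured, and these items are collected.

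**Conclusion.** The concern holds in limited form. Within DVT, PE and combined events, the main model has no measure of acute severity or care setting, and Table 7.6: 2 omits index event too. The protocol collects items that could fill the gap, and its own selection rule for the propensity model points towards considering them. The documents show that both main hazard ratios are exposed to this confounding. They do not show that it is present, how large it is, or which drug it would favour.

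A reader might infer that the comparison will be biased towards dabigatran. That would need admission or severity rates by arm, which the documents do not give. The shifts of 0.88 to 0.96 rest wholly on assumed prevalences and rate ratios and are upper figures if existing covariates capture part of the same imbalance. At the planned bleeding event count they amount to roughly 0.3 to 1.1 standard errors: enough to colour the reading of a modest effect, not enough alone to produce the planned 0.69. The change is worth making because it uses data already collected and costs little.

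**What to change.** 1. Add to Table 7.6: 1 thrombus location, extent and severity; admission for the index event (yes/no, when it precedes first dabigatran or VKA intake); systolic blood pressure; and heart rate. Use only values dated on or before first intake, as SAP Section 6.7 requires. Derive admission from the discharge record with a stated rule, because the protocol's data list gives a discharge date but no admission date.
2. Include these items in the multiple imputation in Section 6.6, which at present names only alcohol, BMI, creatinine clearance and smoking.
3. Name them among the covariates of interest for the unweighted and weighted standardized differences.
4. Add index event to Table 7.6: 2, and the other items where event numbers allow, given the convergence caveat in Section 7.6.
5. If pre-treatment vital signs are too incomplete to impute, keep admission and thrombus severity in the model and report the weighted balance of the vital signs that were observed.

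Cost: a date-check rule, more imputation, and a slightly lower effective sample size after weighting. No new data collection is needed.

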Optimal treatment duration for acute VTE and the secondary prevention of recurrent VTE is not definitively known. The two terms “acute treatment” and “secondary prevention” are not precisely defined and might overlap. Current guidelines recommend treatment for 3 months over shorter treatment durations [[P12-01518](#), [P14-16368](#)]. An extended duration of anticoagulation treatment should be considered for those patients with the greatest risk of VTE recurrence, i.e., those with an unprovoked DVT and/or PE; recurrent VTE, co-morbidities, such as cancer, chronic inflammation of the peripheral veins, and a strong genetic pre-disposition to thrombosis.

For patients with a chronic risk of recurrent VTE, there is evidence that when oral anticoagulation therapy is stopped, the risk of recurrence will increase to pre-treatment levels [[P08-08095](#), [R09-4888](#)]. Therefore, the decision to continue treatment for prevention of recurrent VTE must consider the risk factors for recurrence as well as any risk factors for bleeding. The risk of bleeding increases in patients with a prior history of bleeding events, the presence of certain co-morbidities (e.g., gastrointestinal ulceration, inflammation or malignancy or other metabolic disorders that might alter hemostasis such as cirrhosis or chronic renal disease or concomitant medications that alter hemostasis (i.e. antiplatelet agents)). These risks must be reviewed periodically, and therefore, treatment decisions should be individualized and periodically reviewed.

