The efficacy and safety of dabigatran etexilate versus (vs) warfarin has been tested in 4 pivotal, randomized, double-blind, clinical trials. A dose of 150 mg b.i.d. of dabigatran etexilate was tested in all 4 trials. Two trials (RE-COVER and RE-COVER II) demonstrated that dabigatran etexilate was non-inferior to warfarin for treatment of acute VTE [[U09-1400](#), [U11-2298](#)]. Two other trials focused on secondary prevention in high-risk (RE-MEDY) [[U10-2533](#)] and lower risk (RE-SONATE) patients [[U11-2267-02](#)]. Dabigatran etexilate was non-inferior to warfarin in secondary prevention of recurrent VTE events in high-risk patients and superior to placebo in lower risk patients. The safety profile of dabigatran etexilate from the pivotal studies is consistent with the available safety data from other indications. The most common related adverse events (AE) for dabigatran etexilate included bleeding and GI AEs (e.g., dyspepsia and gastritis) however, dabigatran etexilate had fewer major or clinically relevant bleeding events compared to warfarin.

The safety of dabigatran etexilate vs warfarin in VTE patients has not been assessed in routine clinical practice. However, dabigatran etexilate safety has been assessed in patients being treated for nonvalvular AF in a study of elderly Medicare patients [[P14-15648](#)]. A total of 67,494 dabigatran etexilate patients and 273,920 warfarin patients were eligible for the study. Compared with warfarin, dabigatran etexilate use was associated with a reduced risk of ischemic stroke, intracranial hemorrhage, and mortality but with an increased risk of gastrointestinal bleeding. The increased risk of gastrointestinal bleeding occurred in women aged  $\geq 75$  years and to men aged  $\geq 85$  years.

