#### **9.7.2.1 Main analyses**

For Objective 1:

Baseline patient demographics and disease characteristics, including information regarding the index VTE event, medical history, concomitant therapies, and laboratory data as specified in [Section 9.3.1](#), will be summarized descriptively for all eligible patients overall and by anticoagulation treatment at baseline. The analysis will be repeated by region and by additional relevant patient attributes.

Patterns of anticoagulation treatment at baseline will be described overall, by region, and by additional relevant patient attributes.

For Objective 2:

Patient demographics and disease characteristics at baseline as described above for Objective 1 will be summarized descriptively for all eligible patients by their initial anticoagulation treatment (i.e. dabigatran etexilate or VKA). This analysis will be repeated by region and by additional relevant patient attributes.

Given the observational nature of this study, patients in the dabigatran etexilate and VKA groups may differ with regard to important baseline demographics and disease characteristics. When the target sample size is reached, propensity scores that estimate the probabilities that patients would be initiated on dabigatran etexilate will be calculated using a logistic regression model that considers variables that are risk factors for the occurrence of VTE or bleeding events or affect the choice of anticoagulation treatment (details of the model will be provided in the SEAP). Overlap of propensity scores between the dabigatran etexilate and VKA groups will be examined to assess the comparability of the two patient populations, and to estimate the loss of patients from the comparative analysis if trimming or matching is to be performed.

The primary safety and effectiveness outcomes will be analyzed for dabigatran etexilate patients in comparison to VKA patients using Cox proportional hazards models. Confounding will be controlled for using appropriate methods, including adjustment of covariates in the Cox regression model, trimming of extreme observations, and/or propensity score matching, based on the evaluation of the comparability of dabigatran etexilate and VKA patients (i.e. overlap of propensity scores) as described above. Details of the analytical methods and the selection rules of the appropriate analysis strategy will be provided in the SEAP.

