Baseline variables will be included in the model based on their known/suspected association with the main outcome events. As suggested by the literature, only confounders or variables associated with the outcomes will be considered. Table 7.6: 1 summarizes the identified variables to be included in the logistic regression model based on these criteria. In the event of non-convergence, investigations will be done to explore the most likely reason and to aggregate or exclude the responsible variables. Generally, all missing values of variables which will be included in the logistic regression model will be imputed according to Section 6.6.

Table 7.6: 1 Variables for PS model

Variable	Comment	Potential for missing values and implications
Age group	<65, 65 to <75, >=75	Very unlikely
Sex	Male, Female	Rare
BMI	<18.5, 18.5 to <25, 25 to <30, 30 to <35, ≥35, missing	Missing will be imputed
Creatinine clearance	<30, 30 to < 50, 50 to <80, ≥80, missing	Missing will be imputed
Region	Europe, Middle East, North America, Latin America, Asia, Other	Very unlikely
Smoking status	non-smoker, current smoker, past smoker, unknown	Rare – will impute missing and unknown values
Alcohol use	Never, < 1 drink/week, 1-7 drinks/week, ≥8 drinks/week, unknown	Rare – will impute missing and unknown values
Trauma or surgery	True or False (CRF categories, medical history and concomitant diseases will be manually reviewed – 3 month time window)	N/A
Immobilization	True or False (CRF categories, medical history and concomitant diseases will be manually reviewed (past and concomitant))	N/A
Obesity	True or False (CRF categories, medical history and concomitant diseases will be	N/A

	manually reviewed (past and concomitant))	
Thrombophilia	True or False (CRF categories, medical history and concomitant diseases will be manually reviewed (past and concomitant))	N/A
Pregnancy and peri-partum period	True or False (CRF categories, medical history and concomitant diseases will be manually reviewed (3 month time window))	N/A
Concomitant use of aspirin	True or False (concomitant medication and other VTE therapies will be manually reviewed (concomitant))	N/A
Concomitant use of clopidogrel	True or False (concomitant medication and other VTE therapies will be manually reviewed (concomitant))	N/A
Estrogen therapy	True or False (concomitant medication and other VTE therapies will be manually reviewed (3 month time window))	N/A

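### Gastrointestinal ulceration and inflammation, which the protocol names as bleeding risk factors, have no term in either adjustment model, so the primary bleeding comparison is open to avoidable residual confounding

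*SAP*

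**What the plan says.** Protocol section 7.2 (Treatment Options) says that bleeding risk rises with prior bleeding, with "certain co-morbidities (e.g., gastrointestinal ulceration, inflammation or malignancy or other metabolic disorders that might alter hemostasis" (cirrhosis and chronic renal disease are the examples), and with drugs such as antiplatelets. The same section reports that the most common related adverse events on dabigatran were "bleeding and GI AEs (e.g., dyspepsia and gastritis".

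Protocol section 9.7.2.1 describes a propensity model that "considers variables that are risk factors for the occurrence of VTE or bleeding events or affect the choice of anticoagulation treatment". The Objective 2 SAP, section 7.6, states its own rule: "Baseline variables will be included in the model based on their known/suspected association with the main outcome events".

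Table 7.6: 1 lists the propensity covariates. The gastrointestinal row is "Prior gastrointestinal bleed", and history of major bleeding is a separate row. Table 7.6: 2, for the sensitivity Cox model, merges these two into one row. Neither table has a row for ulcer, gastritis or other gastrointestinal inflammation.

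Protocol section 9.3.1.1 collects medical history, concomitant diseases, and risk factors "for VTE re-occurrence and risk factors for bleeding". SAP section 7.2 codes history and concomitant diseases in MedDRA. Both model tables fill most of their true/false rows by manual review of those fields.

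**The concern.** A factor that raises bleeding risk and also influences the choice between dabigatran and VKA confounds the primary safety comparison unless it is balanced. The protocol states the first half for gastrointestinal ulceration and inflammation. The second half is plausible, because a prescriber may weigh gastrointestinal history when choosing a drug with known gastrointestinal effects.

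Overlap weights give no assurance of balance on a variable that is left out of the propensity model. The sensitivity Cox model has the same gap, so agreement between the two analyses would not be reassuring on this point. At stake is the reading of the hazard ratio for major plus clinically relevant non-major bleeding, the primary safety outcome of a post-authorisation safety study.

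**Working it through.** **1. Match the protocol's list to the two tables.**

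| Risk factor in protocol 7.2 | Table 7.6: 1 (propensity) | Table 7.6: 2 (Cox) |
|---|---|---|
| Prior bleeding | Major bleeding; prior GI bleed | The two combined |
| GI ulceration, inflammation | None | None |
| Malignancy | Concomitant cancer | Concomitant cancer |
| Cirrhosis | Chronic hepatic disease | None |
| Chronic renal disease | Chronic renal disease; creatinine clearance | Chronic renal disease |
| Antiplatelet drugs | Aspirin; clopidogrel | Aspirin; clopidogrel |

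In the propensity table, ulceration/inflammation is the only specific example without a term.

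**2. What omission means under overlap weights.** Let Z = 1 for dabigatran and P be the fitted score. A logistic fit satisfies Σ(Z − P)x = 0 for each covariate x in the model. This rearranges to ΣZ(1 − P)x = Σ(1 − Z)Px, which is equality of the overlap-weighted totals. Covariates in the model are therefore balanced (exactly before trimming and averaging over imputations, closely afterwards). A covariate outside the model is balanced only as far as it correlates with those inside.

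**3. The plan's own figure, to set a scale.** Protocol Table 9.5:2 gives 5000 patients for HR 0.69, 90% power, one-sided alpha 0.025, VKA rate 7.7% and 15% loss.
- Hazards: λ = −ln(1 − 0.077) for VKA, and η = −ln(0.85) for exponential loss.
- Probability of an observed event in one year: λ/(λ + η) × [1 − exp(−(λ + η))].
- Freedman events: (1.96 + 1.28)² × [(1 + HR)/(1 − HR)]².
- At HR 0.685, which rounds to 0.69 and gives a dabigatran rate of 5.34%: 300.7 events and N = 4991. The stated 5000 reproduces.
- At HR 0.69 exactly and N = 5000: about 302 events and 89.0% power.

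So SE(log HR) ≈ 2/√302 = 0.115. Weighting and as-treated censoring would make it larger.

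**4. Possible bias, on assumed inputs.** The documents give no prevalence for these conditions and no rate ratio for bleeding. For one unadjusted binary factor with prevalence p in each group and bleeding rate ratio R:

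factor on the HR = [1 + p_DE(R − 1)] / [1 + p_VKA(R − 1)]

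| p_DE vs p_VKA | R = 1.5 | R = 2 | R = 3 |
|---|---|---|---|
| 2% vs 4% | 0.990 | 0.981 | 0.963 |
| 5% vs 5% | 1.000 | 1.000 | 1.000 |
| 5% vs 10% | 0.976 | 0.955 | 0.917 |
| 5% vs 15% | 0.953 | 0.913 | 0.846 |
| 10% vs 5% | 1.024 | 1.048 | 1.091 |

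The mirror of the most extreme case, 15% vs 5% with R = 3, is 1.30/1.10 = 1.18.

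A true HR of 0.69 would appear as 0.58 (0.69 × 0.846) to 0.75 (0.69 × 1.091). In standard errors of log HR, 0.955 is ln(0.955)/0.115 = −0.40, 0.917 is −0.75 and 0.846 is −1.45.

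These are upper bounds in spirit. The p should be prevalences remaining after weighting, and R should be conditional on the other covariates. Prior bleeding, age, alcohol, smoking, antiplatelets, cancer, and hepatic and renal disease should absorb part of the effect.

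**5. Would the balance check catch it?** SAP section 7.6 considers re-estimating the score when an adjusted standardised difference exceeds 0.25. For 5% vs 10% the difference is 0.05/√[(0.0475 + 0.09)/2] = 0.19; for 5% vs 15% it is 0.34. Even if the factor were displayed, an imbalance of the first size would not reach the trigger. The factor needs to be in the model as well as in the display.

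**The case against.** A reader might infer more: that the bleeding comparison is confounded, and in dabigatran's favour, because prescribers steer ulcer patients to VKA. The documents do not support that. They contain no prevalence or prescribing data for these conditions, and equal prevalence gives no bias. The dyspepsia and gastritis in protocol 7.2 are events on treatment, so avoidance of dabigatran is only an inference. The same section reports fewer major or clinically relevant bleeds than with warfarin, and the channelling example in section 9.9 has dabigatran going more often to high-risk patients. Either would push the bias the other way. The increased gastrointestinal bleeding cited there comes from an elderly atrial fibrillation cohort. This part of the objection stands in full, so no direction is claimed here.

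Three further points carry some weight.
- The protocol list is a set of examples in a background section, and inflammation could be read more broadly than gastrointestinal. Even so, it is the protocol's own statement of an association with bleeding, which is what both selection rules ask for.
- Section 9.9 already accepts residual unmeasured confounding, and section 9.7.1 calls the analyses exploratory. Those caveats suit factors that cannot be identified or captured. This one is identified, and fields exist to hold it.
- The public text lacks SAP sections 5.3, 6.4 and 7.7, and the balance check covers covariates of interest without limiting them to Table 7.6: 1. Ulcer history may be summarised there. That would not put it into either model. No case report form is shown either, so how completely ulcer or gastritis is captured is unknown.

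Parsimony is a weak defence. Table 7.6: 1 carries both BMI and obesity, and both creatinine clearance and chronic renal disease. Table 7.6: 2 has 14 covariates against about 300 planned events, although as-treated censoring may reduce that number.

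**Conclusion.** The omission is a fact of the two tables and departs from the plan's own selection rules, with no reason given. The supportable conclusion is that the primary bleeding comparison is open to avoidable residual confounding, with size and direction unknown.

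The illustrative factors, about 0.85 to 1.09 in the tabulated cases and 1.18 for the mirrored extreme, rest wholly on assumed prevalences and rate ratios. They take no credit for correlated covariates already in the models. The outer values need a three-fold imbalance together with a rate ratio of 3. A milder case such as 5% vs 10% with a rate ratio of 2 moves the estimate by 0.4 of a standard error. No sample size or power figure changes. The change is worth making because it is nearly free and removes a gap the protocol itself identifies.

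**What to change.** Define one binary variable: history of, or concomitant, gastrointestinal ulcer or gastrointestinal inflammation (e.g., gastritis), true or false. Derive it by manual review of the medical history, concomitant disease and bleeding-risk fields, as for the existing rows, using data up to the start of dabigatran or VKA.

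- Add it to Table 7.6: 1.
- Add it to the Table 7.6: 2 model for the bleeding outcome. The documents give no ground for adding it to the recurrent VTE model.
- Report its standardised difference before and after overlap weighting.

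If the sponsor prefers to leave it out of the main model, the SAP should state why and report a sensitivity analysis that includes it.

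The cost is one more flag in an existing manual review and one more model term. No new data collection is needed. If the flag proves too sparse, the SAP's existing provisions for non-convergence apply.
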